5.4. EXTENDED RANDOMIZED SET

The Extended randomized (RND) set will contain all patients in the ENR set who were randomized to study medication. For analyses and displays based on RND, patients will be classified according to randomized treatment. Site number [REDACTED] will be included in this population.

5.5. MODIFIED INTENT-TO-TREAT POPULATION

The mITT population will contain all patients in the RND set who received at least one dose (or partial dose) of study medication and patients will be classified according to randomized treatment. The intent-to-treat principle is preserved, despite the exclusion of patients randomized who did not take the study medication, because the decision of whether or not to begin the treatment could not be influenced by knowledge of the assigned treatment, i.e. the study medication is blinded. Site number [REDACTED] will be excluded from this population.

5.6. EXTENDED MODIFIED INTENT-TO-TREAT POPULATION

The Extended mITT population will contain all patients in the RND set who received at least one dose (or partial dose) of study medication and patients will be classified according to randomized treatment. The intent-to-treat principle is preserved, despite the exclusion of patients randomized who did not take the study medication, because the decision of whether or not to begin the treatment could not be influenced by knowledge of the assigned treatment, i.e. the study medication is blinded. Site number [REDACTED] will be included in this population.

5.7. PER-PROTOCOL POPULATION

The per-protocol (PP) population will contain all patients in the mITT who did not discontinue the study medication before study day 74, and did not experience any major/important PDs considered to have an impact on efficacy assessments involving lung function at week 12. Reasons for exclusion will be specified at a BDR meeting prior to DBL and may include violations of inclusion/exclusion criteria, violations of withdrawal criteria, incorrect randomization, use of prohibited medication, did not follow blinding procedures and non-compliance. Patients will be classified according to randomized treatment.

If protocol deviations in terms of dosing errors are detected post unblinding, these will lead to exclusion only if patient has received and used the opposite study drug compared to what was specified in the randomization and that this use occurred prior to week 12.

5.8. SAFETY ANALYSIS SET

The safety analysis (SAF) set will contain all patients in the RND set who receive at least one dose (or partial dose) of study medication and patients will be classified according to treatment received.

If there is any doubt whether a patient was treated or not, they will be assumed treated for the purposes of analysis. Site number [REDACTED] will be excluded from this population.

5.9. EXTENDED SAFETY ANALYSIS SET

The Extended safety analysis (SAF) set will contain all patients in the RND set who receive at least one dose (or partial dose) of study medication and patients will be classified according to treatment received.

If there is any doubt whether a patient was treated or not, they will be assumed treated for the purposes of analysis. Site number [REDACTED] will be included in this population.

5.10. PHARMACOKINETIC SET

The PK analysis set (PKAS) will include all patients randomized to ensifentrine, who receive at least one dose of ensifentrine, and have at least one quantified ensifentrine concentration at a scheduled PK time point after the start of dosing without important protocol violations and/or events with potential to affect PK concentrations.

The population PK analysis set will be defined separately in the modeling data analysis plan prepared by Verona Pharma/Designee.

6. GENERAL CONSIDERATIONS

6.1. REFERENCE DATES AND STUDY DAY

Study Day will be calculated from the reference start date and will be used to show start/stop day of assessments and events.

Reference start date is defined as the day of the first dose of study medication (Day 1 is the day of the first dose of study medication) and will appear in every listing where an assessment date or event date appears.

- If the date of the event is on or after the reference start date, then:
Study Day = (date of event – reference start date) + 1.
- If the date of the event is prior to the reference start date, then:
Study Day = (date of event – reference start date).

In the situation where the event date is partial or missing, the date will appear partial or missing in the listings, and Study Day, and any corresponding durations will be presented based on the imputations specified in Appendix 2 of the SAP.

Reference end date is defined as the date of the last dose of study medication.

6.2. BASELINE

Unless otherwise specified, baseline is defined as the last non-missing measurement taken prior to reference start date (including unscheduled assessments). In the case where the last non-missing measurement and the reference start date coincide, that measurement will be considered baseline, unless time is present. If time of the assessment is on or after the study treatment start date, then the assessment is not considered baseline except in the following case: for main and responder SGRQ analysis, if the assessment on the day of randomization is done after dosing but prior to leaving the clinic after the 4 hour spirometry, the assessment is considered baseline. Adverse Events (AEs) and medications commencing on the reference start date will be considered post-baseline, ECG abnormalities from pre-dose assessments and laboratory abnormalities from pre-dose draws that are analyzed externally post-dose are still considered baseline.

Baseline for the spirometry endpoints is defined as the mean of the 2 measurements taken pre-dose on Day 1 prior to reference start date and time, unless only 1 measurement is taken pre-dose on Day 1 prior to reference start date and time.

If the baseline visit is split across in 2 days with dosing on Day 1, then measurement from day – 1 will constitute baseline for spirometry endpoints.

6.3. RETESTS, UNSCHEDULED VISITS AND EARLY TERMINATION DATA

In general, for by-visit summaries, data recorded at the nominal visit will be presented.

Patients who were a screen failure and received approval from the Medical Monitor for rescreening will go through all of the original screening assessments. Data from the latest rescreened visit will be used in the summaries, however all screening information will be listed. Rescreened patients will keep the same patient number, as for the initial screening. Unscheduled measurements will not be included in by-visit summaries but will contribute to the EOS value, or best/ worst case value where required (e.g. shift table).

Early termination data will be mapped to the next available visit number for by-visit summaries, as described in section 6.4 of the SAP.

Post-randomization if ECG result is Abnormal, Clinically Significant, then triplicate ECGs should be provided.

Listings will include scheduled, unscheduled, retest and early discontinuation data.

6.4. WINDOWING CONVENTIONS

Each visit (except for Day 1 visit) will have a ± 10 days window. No visit windowing will be applied during the analysis to the data that is only collected at scheduled site visits for patients that have completed the study, and therefore the data will be presented as per the visit reported in the database.

For the patients that discontinued from the study, the End of Study (EOS) visit will be windowed to the corresponding visit, based on the study day, for questionnaire, spirometry and rescue medication data. The EOS visit can only be windowed to a visit that is missing or has a missing result. The rules for the windowing are described below.

- For spirometry raw data and derived data that happens at every visit, windowing will be done as per the corresponding visits.

- Day 1 = Day 1
 - Week 6 = after Day 1 and up to and including Day 53
 - Week 12 = after Day 53 and up to and including Day 95
 - Week 24 = after Day 95 and up to and including Day 179
- For spirometry derived data that only happen at certain visits, windowing will be done for the corresponding visits.
 - For morning trough:
 - Week 6 = after Day 1 and up to and including Day 53
 - Week 12 = after Day 53 and up to and including Day 95
 - Week 24 = after Day 95 and up to and including Day 179
 - For evening trough and AUC_{0-12h}:
 - Week 12 = after Day 1 and up to and including Day 95
- For rescue medication data, E-RS/EXACT-PRO, e-diary data and COPD exacerbation, windowing will be done as per the corresponding visits.
 - For patients who completed the study or who discontinued study medication but continue in the study:
 - Week 1 = Actual study Day of Week 24 visit minus 168 days (inclusive) up to and including actual study day of week 24 visit minus 161 days
 - Week 2 = Actual study Day of Week 24 visit minus 161 days up to and including actual study day of week 24 visit minus 154 days
 - Week 3 = Actual study Day of Week 24 visit minus 154 days up to and including actual study day of week 24 visit minus 147 days
 - Week 4 = Actual study Day of Week 24 visit minus 147 days up to and including actual study day of week 24 visit minus 140 days
 - Week 5 = Actual study Day of Week 24 visit minus 140 days up to and including actual study day of week 24 visit minus 133 days
 - Week 6 = Actual study Day of Week 24 visit minus 133 days up to and including actual study day of week 24 visit minus 126 days
 - Week 7 = Actual study Day of Week 24 visit minus 126 days up to and including actual study day of week 24 visit minus 119 days
 - Week 8 = Actual study Day of Week 24 visit minus 119 days up to and including actual study day of week 24 visit minus 112 days
 - Week 9 = Actual study Day of Week 24 visit minus 112 days up to and including actual study day of week 24 visit minus 105 days
 - Week 10 = Actual study Day of Week 24 visit minus 105 days up to and including actual study day of week 24 visit minus 98 days
 - Week 11 = Actual study Day of Week 24 visit minus 98 days up to and

- including actual study day of week 24 visit minus 91 days
- Week 12 = Actual study Day of Week 24 visit minus 91 days up to and including actual study day of week 24 visit minus 84 days
- Week 13 = Actual study Day of Week 24 visit minus 84 days up to and including actual study day of week 24 visit minus 77 days
- Week 14 = Actual study Day of Week 24 visit minus 77 days up to and including actual study day of week 24 visit minus 70 days
- Week 15 = Actual study Day of Week 24 visit minus 70 days up to and including actual study day of week 24 visit minus 63 days
- Week 16 = Actual study Day of Week 24 visit minus 63 days up to and including actual study day of week 24 visit minus 56 days
- Week 17 = Actual study Day of Week 24 visit minus 56 days up to and including actual study day of week 24 visit minus 49 days
- Week 18 = Actual study Day of Week 24 visit minus 49 days up to and including actual study day of week 24 visit minus 42 days
- Week 19 = Actual study Day of Week 24 visit minus 42 days up to and including actual study day of week 24 visit minus 35 days
- Week 20 = Actual study Day of Week 24 visit minus 35 days up to and including actual study day of week 24 visit minus 28 days
- Week 21 = Actual study Day of Week 24 visit minus 28 days up to and including actual study day of week 24 visit minus 21 days
- Week 22 = Actual study Day of Week 24 visit minus 21 days up to and including actual study day of week 24 visit minus 14 days
- Week 23 = Actual study Day of Week 24 visit minus 14 days up to and including actual study day of week 24 visit minus 7 days
- Week 24 = Actual study Day of Week 24 visit minus 7 days up to and including actual study day of week 24 visit
- For patients who discontinue the study before Week 24:
 - Week 1 = on or after Day 1 and up to and including Day 8
 - Week 2 = after Day 8 and up to and including Day 15
 - Week 3 = after Day 15 and up to and including Day 22
 - Week 4 = after Day 22 and up to and including Day 29
 - Week 5 = after Day 29 and up to and including Day 36
 - Week 6 = after Day 36 and up to and including Day 43
 - Week 7 = after Day 43 and up to and including Day 50
 - Week 8 = after Day 50 and up to and including Day 57
 - Week 9 = after Day 57 and up to and including Day 64
 - Week 10 = after Day 64 and up to and including Day 71

- Week 11 = after Day 71 and up to and including Day 78
- Week 12 = after Day 78 and up to and including Day 85
- Week 13 = after Day 85 and up to and including Day 92
- Week 14 = after Day 92 and up to and including Day 99
- Week 15 = after Day 99 and up to and including Day 106
- Week 16 = after Day 106 and up to and including Day 113
- Week 17 = after Day 113 and up to and including Day 120
- Week 18 = after Day 120 and up to and including Day 127
- Week 19 = after Day 127 and up to and including Day 134
- Week 20 = after Day 134 and up to and including Day 141
- Week 21 = after Day 141 and up to and including Day 148
- Week 22 = after Day 148 and up to and including Day 155
- Week 23 = after Day 155 and up to and including Day 162
- Week 24 = after Day 162 and up to and including Day 169

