7.0 DISCONTINUATION OF BLINDED STUDY MEDICATION AND PATIENT DISCONTINUATION/WITHDRAWAL

7.1 Discontinuation of Blinded Study Medication

Patients who permanently discontinue blinded study medication are not required to withdraw from the study unless they test positive for COVID-19 active disease. If a patient must permanently discontinue blinded study medication for reason(s) other than testing positive for COVID-19 active disease, the patient should complete the “Patient Discontinuation/Withdrawal from the Study” assessments described in Section 7.3 as soon as possible. In addition, every effort should be made by the investigator/staff to keep the patient in the study to collect important efficacy and safety data as detailed in Section 7.2.

Circumstances potentially requiring or actually resulting in discontinuation of blinded study medication are described below.

See the SoA (Section 1.3) for data to be collected at the time of treatment discontinuation and follow-up and for any further evaluations that need to be completed.

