7.2.3 Phone Contact Only

The site contacts the patient by phone per the SoA (Section 1.3) to complete the following assessments:

- COPD exacerbation
- SAE
- Concomitant medication

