7.3.1 Early Termination/Withdrawal Procedures

If a patient is withdrawn prior to the Week 12 visit, every attempt should be made to have the patient complete the early termination/ withdrawal procedures in the SoA (Section 1.3) as soon as possible.

- If possible, patients should remain on blinded study medication and their maintenance LAMA or LABA medication and ICS (if applicable), follow the withholding procedures prior to Spirometry in Section 8.3.1.2, and should refrain from smoking or caffeinated beverages as recommended in Section 5.4.1.1.
- Patients unable to remain on blinded study medication and/or their maintenance LAMA or LABA medications and ICS (if applicable) should still complete the early termination/ withdrawal visit as soon as possible.

7.3.1.1 12-Hour Spirometry and 1.5 Hour ECG Procedures

For patients who are withdrawn prior to completing the Week 12 visit only, every attempt should be made to have the patient complete the 12-hour spirometry procedures and the ECG procedures at the early termination/withdrawal visit unless consent is withdrawn or the patient is being withdrawn for safety reasons precluding this assessment.

Patients who Continued Blinded Study Medication

Patients who have continued administration of their blinded study medication should complete the spirometry and ECG procedures as follows:

- Spirometry: Pre-dose and 0-12-hour post-dose assessments as per Section 1.4 and Section 8.3.1.
- ECG: Pre-dose and 1.5-hour post-dose ECG procedures as per Section 8.4.2.

Patients who Discontinued Blinded Study Medication

Patients who have discontinued blinded study medication prior to the early termination/withdrawal visit may optionally complete spirometry and ECG assessments at the early termination visit if they have not already completed the Week 12 assessments. These patients will not be dosed with blinded study medication. If possible, patients should start spirometry between 6 am and 10am, withhold rescue medication and/or maintenance LAMA or LABA medications for the time period specified in Section 6.7.2, and refrain from caffeinated beverages and/or smoking for the time period specified in Section 5.4.1. The spirometry and ECG procedures should be completed as follows:

- Spirometry: Serial spirometry at 0-hour, 30 min, and 1, 2, 4, 6, 8, and 12 hours.
- ECG: 12-lead ECG at 0-hour and 1.5 hours.

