9.0 STATISTICAL CONSIDERATIONS

9.1 Statistical Hypotheses

The aim of this study is to show superiority of ensifentrine over placebo regarding selected efficacy measures. The null hypothesis to be tested for each endpoint will be that there is no difference between ensifentrine and placebo, against the alternative hypothesis that ensifentrine is better than placebo. All tests will be two-sided at a 5% significance level. Primary and key secondary endpoints used for claims will be tested in a sequential order to preserve the alpha level. Testing will stop once a not significant result is achieved. Test order will be FEV₁ AUC_{0-12h} at 12 weeks, peak FEV₁ at 12 weeks, weekly mean E-RS total symptom score at week 24, SGRQ total score at Week 24, morning trough FEV₁ at Week 12, FEV₁ AUC_{0-4h} at 12 weeks and proportion of SGRQ responders at 24 weeks.

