9.2 Sample Size Determination

Approximately 800 patients will be randomized. The standard deviation for the change in FEV₁ AUC_{0-12h} is estimated to be 250 mL. With a 2-sided test at a 5% significance level and 500 vs. 300 evaluable patients in the two groups, there will be an 90% power to detect a true difference of 59 mL between the treatments. If the withdrawal rate at 24 weeks exceeds 25% overall, additional patients may be randomized to the study to compensate for the loss of data.

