9.4 Statistical Analyses

9.4.1 Efficacy Analyses

Efficacy analysis will primarily be performed on the mITT population. The primary endpoint and key secondary endpoints will also be evaluated using the PP population as a sensitivity analysis. Impact of imputations and various baseline characteristics will also be checked.

The primary endpoint, change from baseline in FEV₁ AUC_{0-12h} at Week 12, will be compared between treatments using an analysis of covariance (ANCOVA) model adjusting for treatment, region, background medication strata, and smoking status as factors and baseline FEV₁ as covariate. The estimated treatment difference with 95% confidence interval and associated (two-sided) p-value will be presented. Missing data will be imputed to get as close to the mITT population as possible. Primarily imputation will be based on data collected at visits performed after treatment withdrawal or at early termination visits even if outside visit window. When no such data is available, imputation will primarily be done using multiple imputation based on baseline characteristics and secondarily, as a sensitivity analysis, by the average change in the opposite treatment group as randomized to as a worst-case scenario. Further details on the handling of missing data will be given in the Statistical Analysis Plan.

Key secondary endpoints, FEV₁ AUC_{0-4h}, peak FEV₁, morning trough FEV₁, SGRQ total score and weekly mean E-RS total score, and other continuous secondary or exploratory endpoints will be assessed repeatedly during the study and the change from baseline to pre-specified time point of evaluation will be compared by similar ANCOVA models adjusting for treatment, region, background medication strata and smoking status as factors and baseline as covariate. Data collected at visits performed after treatment withdrawal or at early termination visits will be used in the analyses. Remaining missing data will primarily be imputed using multiple imputation based on baseline characteristics and data collected at post-randomization visits. Since assessed repeatedly, in contrast to primary endpoint, these data will also be analyzed for sensitivity by mixed model repeated measures models with treatment, visit and treatment by visit interaction as factors, baseline as covariate, subject as random factor and covariance structure by visit.

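### Protocol 9.4.1 uses early-termination data for the primary endpoint before imputing, but SAP 6.4 and 7.3, read literally, assign no analysis visit to that 12-hour series when the patient stops drug and stays in the study

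*SAP*

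**What the plan says.** **Protocol.** Section 7.1 asks a patient who permanently stops drug, other than for COVID-19, to complete the "assessments described in Section 7.3 as soon as possible", and asks sites to keep that patient in the study. Before Week 12, Section 7.3.1.1 provides a 12-hour spirometry series at that visit. Every attempt is to be made to obtain it if the patient is still dosed. Patients who have already stopped "may optionally complete spirometry and ECG assessments at the early termination visit if they have not already completed the Week 12 assessments". Afterwards the patient may be followed by phone only (7.2.3: "The site contacts the patient by phone per the SoA (Section 1.3) to complete the following assessments", with no spirometry among them) or by phone plus a Week 24 clinic visit (7.2.2). Neither option includes Week 12 spirometry.

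Section 9.4.1 says missing primary data are first filled "based on data collected at visits performed after treatment withdrawal or at early termination visits even if outside visit window", with multiple imputation only when no such data exist. Section 9.4.4 adds that everything collected after treatment withdrawal is used.

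**SAP.** Section 6.4 states: "For the patients that discontinued from the study, the End of Study (EOS) visit will be windowed to the corresponding visit". The rule covering AUC0-12h (after Day 1 to Day 95 = Week 12) sits under that sentence. Section 7.3 admits to the mITT analysis the scheduled visits, on or off treatment, plus the end-of-study visits of patients withdrawing from the study. Section 6.3 maps early-termination data more generally, but only for by-visit summaries and by reference to 6.4. Section 3.3 lists no change on this point.

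**The concern.** One group falls between the SAP's categories: patients who stop drug before Week 12, give the 12-hour series at the early-termination visit, stay in the study and do not attend Week 12 spirometry. They have not left the study, so 6.4 gives that visit no window and 7.3 does not admit it. It is their only post-baseline 12-hour series. The protocol would use it; the SAP as written imputes over it.

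The primary estimand is treatment policy (SAP 2.5). The primary imputation model (SAP 16.1.2) contains treatment, region, the two strata, baseline FEV1 and the Week 12 AUC0-12h. It has no other post-baseline visit and no indicator for being off drug. The imputed value is therefore a draw from the randomised arm given baseline.

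There is a smaller diary problem. For patients who stop drug but continue, SAP 6.4 counts every diary week back from the Week 24 visit, which a phone-only patient does not have. Weekly E-RS at Week 24 is third in the testing order.

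**Working it through.** **1. The plan's own figure.** Protocol 9.1: "All tests will be two-sided at a 5% significance level". Protocol 9.2: the SD "is estimated to be 250 mL", and with "500 vs. 300 evaluable patients in the two groups, there will be an 90% power to detect a true difference of 59 mL".

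- SE = 250 × √(1/500 + 1/300) = 18.3 mL
- Power = Φ(59/18.26 − 1.96) = Φ(1.27) = 89.8%, which agrees with the stated 90%.

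**2. Which patients have a rule.** Each row is a patient who stopped drug before Week 12 and gave the early-termination series.

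| What happens next | Source of Week 12 AUC0-12h under the SAP |
|---|---|
| Leaves the study | Early-termination series, windowed by 6.4 and admitted by 7.3 |
| Stays, attends Week 12 off drug | Scheduled Week 12 visit, admitted by 7.3 |
| Stays, phone plus Week 24 (7.2.2) | No rule for the series; imputed |
| Stays, phone only (7.2.3) | No rule for the series; imputed |

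The wording of 6.4 is not easily read as loose. Its diary rules name patients who stopped medication but continue, group them with completers, and list patients who discontinue the study separately.

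**3. Size if the series was undosed.** Let p be the share of the ensifentrine arm on this path with an undosed series. Assume that the true off-drug benefit is zero and that imputed values carry the full planned benefit. Then

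overstatement = p × 59 mL.

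| p (assumed) | Overstatement | As a fraction of SE (18.3 mL) |
|---|---|---|
| 1% | 0.6 mL | 0.03 |
| 2% | 1.2 mL | 0.06 |
| 5% | 3.0 mL | 0.16 |
| 10% | 5.9 mL | 0.32 |

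Placebo patients on this path add nothing under these assumptions, because they have no drug effect to lose.

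**4. Size if the patient was still dosed.** The lost value is on-drug and the imputed draw comes largely from patients on drug, so no direction of bias follows. What is lost is information. If a share f of all series is lost equally from both arms and imputation recovers nothing, power at 59 mL is 89.5% for f = 1%, 89.2% for 2%, 88.3% for 5% and 86.6% for 10%.

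Every value of p and f here is an assumption. The documents give no count for this path.

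**The case against.** The strongest reply is that the intent to use these data is plain. Protocol 9.4.4 says so. SAP 6.3 maps early-termination data without restriction by study status. SAP 16.1.4 has an observed-data analysis that takes patients on or off treatment, at the required timepoint or at the end-of-study visit, and SAP 16.1.2 refers to the early-termination visit in its average imputation. Protocol 4.4 also counts as completers only those who finish all on-treatment visits, so a permanent drug-stopper is not clearly barred by the sentence on completers in 6.4. This stands to the extent that the SAP contains no explicit instruction to discard the series. It does not close the gap: 6.3 is confined to by-visit summaries and defers to 6.4, Sections 16.1.2 and 16.1.4 do not define the visit for patients who stay in, and 7.3, which governs the mITT analysis, repeats the limit.

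A reader might infer that the gap favours ensifentrine in general. The documents do not support that. Protocol 7.3.1 and footnote 4 of the Schedule of Activities ask that patients remain on drug through the early-termination visit where possible, and the undosed series is optional. Many of these series may therefore be on-drug. Nor does the 25% withdrawal trigger in Protocol 9.2 indicate how many patients follow this path. The ensifentrine data behind the imputation also include off-drug Week 12 visits and early-termination values of study withdrawals, so the imputed benefit may be below 59 mL. The tipping-point analysis separately stresses imputed values.

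On the diary, SAP 16.2.1.2.1 and 16.2.1.3 substitute an end date for patients who discontinued. The eDiary is collected at the early-termination visit, and the reduced and phone options list no diary, so little later diary data is expected. That narrows the point. But the two sections use differently worded end dates, and neither says how it fits the count back from Week 24 for someone still in the study.

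**Conclusion.** The point holds as a mismatch between protocol and SAP on the primary endpoint. Followed literally, the SAP imputes a Week 12 AUC0-12h for patients whose early-termination series the protocol says to use first, and 3.3 does not declare the change.

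The effect is probably modest and its size is unknown. For undosed series the overstatement is at most p × 59 mL, given zero off-drug benefit and imputed values carrying the full planned effect; at an assumed p of 5% that is 3.0 mL, or 0.16 of the planned standard error. For dosed series the consequence is lost data and a departure from the protocol, without a clear direction of bias. Planned sample size and power are not in question. The diary part is a smaller ambiguity limited to patients who stay in without a Week 24 visit. The change is worth making because it is cheap and concerns the primary analysis.

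**What to change.** In SAP 6.4 and 7.3, apply the existing end-of-study windowing (for AUC0-12h, after Day 1 to Day 95 = Week 12) also to the early-termination visit of patients who permanently stopped drug but stayed in the study. Apply it only when the scheduled visit has no value, so a Week 12 measurement always takes precedence. Align 6.3, 16.1.2 and 16.1.4 so that each names the same visit for the same patients. For undosed series, also state in 16.1.1.1 that the 0-hour reading serves as time 0, since that section calculates no AUC without a pre-dose value.

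For patients who stay in the study but have no Week 24 visit, use the fixed-day diary windows that 6.4 already lists for study withdrawals, and reconcile this with 16.2.1.2.1 and 16.2.1.3.

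The cost is SAP wording and a small change to the windowing program; no new data are needed. The downside is that some values carried to Week 12 will come from on-drug visits before Week 12, in patients who are off drug by then. Protocol 9.4.1 already accepts this for study withdrawals.

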9.4.4 Missing Data

All data collected after treatment withdrawal will be used in the analyses. Patients withdrawn from study will perform an End-of-Study visit after decision to withdraw the patient has been made. Data collected at such visits will be used for analysis even if outside the visit window for the endpoint. Remaining missing data will primarily be imputed using multiple imputation based on baseline characteristics and data collected at post-randomization visits. In addition, a worst-case scenario using the average change in the opposite treatment group will be used for imputation as a sensitivity analysis. For the responder analysis of SGRQ, patients with no available data for imputation will be considered non-responders as a sensitivity analysis. In exacerbation analyses, patients are included with data collected up to last day in the treatment period/period of recording following treatment withdrawal.

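### SAP 6.4 gives no analysis visit to peak FEV1, AUC0-4h and morning trough from a withdrawal visit held after a completed Week 6 and by Day 53, although AUC0-12h from the same session is used at Week 12

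*SAP*

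**What the plan says.** SAP 6.4 governs patients who discontinue from the study: "the End of Study (EOS) visit will be windowed to the corresponding visit, based on the study day". It then restricts this: "The EOS visit can only be windowed to a visit that is missing or has a missing result".

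The day limits differ by parameter:

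- Spirometry derived at every visit (which covers peak FEV1 and AUC0-4h) and morning trough: "Week 6 = after Day 1 and up to and including Day 53" and "Week 12 = after Day 53 and up to and including Day 95".
- Evening trough and AUC0-12h: "Week 12 = after Day 1 and up to and including Day 95".

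Four other places bear on the same data:

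- SAP 6.3: "Early termination data will be mapped to the next available visit number for by-visit summaries", with a cross-reference to 6.4.
- SAP 7.3: data from the end-of-study visits of withdrawn patients are used in the mITT analysis, and only what is still missing is imputed.
- Protocol 9.4.4, on End-of-Study visits: "Data collected at such visits will be used for analysis even if outside the visit window for the endpoint".
- Protocol 9.4.1: early termination data are used for the key secondary endpoints, and multiple imputation is for the remaining gaps.

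SAP 3.3, which lists changes from the protocol, does not mention the empty-visit restriction.

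**The concern.** SAP 16.1.1.1 schedules the same spirometry at early termination as at Week 12: pre-dose, then 30 minutes to 12 hours. One session therefore yields peak FEV1, morning trough, AUC0-4h, AUC0-12h and evening trough. Protocol 7.3.1.1 asks sites to try hard to obtain it from patients withdrawn before Week 12.

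Under 6.4 the results of that session can be separated. The first four hours contribute to the primary endpoint at Week 12, yet AUC0-4h over those same hours is set aside and imputed at Week 12. Peak FEV1, morning trough and AUC0-4h at Week 12 are steps 2, 5 and 6 of the hierarchy in SAP 7.4, and step 2 stands ahead of E-RS and SGRQ. The estimand in SAP 2.5 is treatment policy, under which a value observed at withdrawal should not give way to a missing-at-random (MAR) imputation when the protocol says it will be used.

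**Working it through.** **The plan's own figures.** SAP 6.4 states the visit tolerance: "Each visit (except for Day 1 visit) will have a ± 10 days window". With nominal day = 7 × week + 1, the window ends are 43 + 10 = 53, 85 + 10 = 95 and 169 + 10 = 179, as SAP 6.4 has them. The 59 mL used below as a yardstick also reproduces (protocol 9.2: SD 250 mL, 500 vs 300, two-sided 5%):

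- SE = 250 × √(1/500 + 1/300) = 18.26 mL
- power = Φ(59/18.26 − 1.960) = Φ(1.272) = 0.898, against the stated 90%

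**Applying 6.4 literally** (study-day window, then the empty-visit condition):

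| EOS day | Already done | Peak, AUC0-4h, morning trough | AUC0-12h, evening trough |
|---|---|---|---|
| 30 | nothing | Week 6 | Week 12 |
| 50 | Week 6 | no visit | Week 12 |
| 53 | Week 6 | no visit | Week 12 |
| 54 | Week 6 | Week 12 | Week 12 |

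In the second and third rows, sending the blocked values to the next empty visit would put them at Week 12, where AUC0-12h already is.

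**Length of the gap.** Days in the gap = 53 − (day of the Week 6 visit):

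- Week 6 on Day 33: Days 34 to 53, 20 days
- Week 6 on Day 43: Days 44 to 53, 10 days
- Week 6 on Day 53: none

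**Number of patients.** The documents give no withdrawal timing, so these counts rest on assumptions, including that every such patient attends and completes the spirometry.

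- Assume 5% to 10% of 800 (40 to 80) withdraw before Week 12, evenly over 84 days, with Week 6 on Day 43. The share in the gap is 10/84 = 11.9%. 0.119 × 40 = 4.8 and 0.119 × 80 = 9.5, so about 5 to 10 patients.
- A wider range: 10% to 25% withdraw evenly over 168 days, with a gap of 10 to 20 days. 800 × 0.10 × 10/168 = 4.8 and 800 × 0.25 × 20/168 = 23.8, so about 5 to 24 patients (0.6% to 3.0%). The 25% is the level at which protocol 9.2 allows extra patients, not a forecast.

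**Effect on an estimate.** As an extreme case, suppose every affected ensifentrine patient has a true effect of zero but is imputed at the full 59 mL. The shift is 59 × affected fraction. Over the wider range this is 59 × 0.10 × 10/168 = 0.35 mL to 59 × 0.25 × 20/168 = 1.76 mL, or about 0.4 to 1.8 mL.

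**The case against.** Much can be said for the plan.

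- **6.3 against 6.4.** A reader might infer that these sections flatly contradict each other. They do not: 6.3 concerns by-visit summaries and defers to 6.4, and its next available visit could be read as the next empty one. No sentence says the values are discarded; that follows from the windows. What stands is that 6.4 starts Week 12 after Day 53 for these parameters and has no rule for moving a blocked value, so the intention in 6.3 is not carried out.
- **The windows differ for a reason.** AUC0-12h is scheduled only at Week 12, so an earlier withdrawal curve has nowhere else to go. The other parameters have a Week 6 slot. That explains the design but not what happens when the slot is taken.
- **A second gap after Week 12.** A reader might infer that an EOS visit after a completed Week 12 and by Day 95 loses its spirometry in the same way. Protocol 7.3.1.1 and 7.3.1.2 plan 12-hour spirometry at withdrawal only for patients who have not completed Week 12, apart from an optional catch-up when it was missed there. That gap is largely empty, and no Week 24 spirometry endpoint is in the hierarchy.
- **All troughs.** Evening trough shares the AUC0-12h window and is kept. Only morning trough is affected.
- **Attendance.** Protocol 7.3.1.1 exempts patients who withdraw consent or leave for safety reasons that preclude the assessment, and makes spirometry optional for those already off drug. The counts above are therefore on the high side for any given withdrawal rate.
- **Mitigation.** The imputation model in SAP 16.2.2.1 uses all scheduled visits, so a recent Week 6 value informs Week 12. The key secondaries also get tipping-point and average-imputation analyses, and the latter draws on early termination data (SAP 16.1.2, 16.2.2.4). This reduces the consequence but does not make the main analysis follow the protocol.

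**Conclusion.** The point holds in a narrow form. For a patient with Week 6 done and an EOS visit with serial spirometry by Day 53, SAP 6.4 as written sends AUC0-12h and evening trough to Week 12 and leaves peak FEV1, AUC0-4h and morning trough without an analysis visit. Their Week 12 values are imputed although they were measured. This conflicts with protocol 9.4.4 and 9.4.1 and with SAP 7.3, and is not declared in SAP 3.3.

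The size is small: no patients if Week 6 was on Day 53, and roughly 5 to 10 under 5% to 10% pre-Week 12 withdrawal, even timing and full completion of the spirometry. Even the wider range and the extreme imputation case move a 59 mL difference by no more than about 1.8 mL. A reader might infer a threat to the primary result; there is none, because the primary endpoint keeps the observed data. The reason to act is that three tests in the hierarchy should follow the stated handling of withdrawal data, and that two programmers reading 6.3 and 6.4 could build different datasets.

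**What to change.** Add to SAP 6.4:

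> For patients who withdraw after a completed Week 6 visit and before a Week 12 visit, EOS spirometry up to Day 53 is assigned to Week 12 for peak FEV1, AUC0-4h and morning trough, as for AUC0-12h.

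Do not extend the roll-forward to Week 24. With Week 12 done as early as Day 75, a general rule could label a visit on Day 76 as Week 24, about 13 weeks early ((169 − 76)/7 = 13.3). If the restriction is intended, the alternative is to list and justify it in SAP 3.3.

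The cost is one sentence and a small derivation change before database lock; sample size and power are unaffected. The downside is that a few values measured several weeks before Week 12 enter the Week 12 secondary analyses, as already happens for the primary endpoint. The change does not touch patients whose Week 6 is missing. Their EOS values still fill Week 6, and their Week 12 secondaries are still imputed while AUC0-12h is observed.
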